Investigational sites	Up to 10 centers in Europe and Israel are planned to participate in this study.
Duration of Subject Participation	Each subject will be followed from pre-treatment to 6 months. After discharge, subjects will come for a clinic visit at 4-6 weeks and at 6 months post implantation.
Primary Endpoint	Absence of CSF fistula (drainage from wound or sinus) and pseudo-meningocele within 6 months post-operative as evaluated by MRI imaging.
Secondary Endpoints	
1. Wound healing assessment2. Device Handling Characteristics (i.e., Ease of Use, strength Suturability, Seal Quality)3. Magnetic Resonance Imaging at the 6-month follow-up, to determine the presence or absence of the following measures:
• Adhesion formation• New tissue formation• Brain edema adjacent to device implant site
Inclusion Criteria	
1. Subject between the ages of 18-752. Subject is scheduled for an elective cranial surgery with a dural damage that can be completely repaired/closed by a suturable dural substitute (ArtiFascia device or other commercially available dural substitutes)3. Subject has undergone imaging (such as, MRI) in the past 6 months before enrolment4. Surgical wound is expected to be Class I/clean5. Subject understands the study requirements and the treatment procedures and provides written Informed Consent before any study-specific tests or procedures

are performed

6. Subject is able and willing to adhere to the required follow-up visits and testing
- Exclusion Criteria**
 1. Pregnant women or interest in becoming pregnant during the duration of the study
 2. Subject has known hydrocephalus
 3. Subject is unable to undergo MRI after the surgery
 4. Subject's life expectancy is less than 12 months
 5. Subject has a local or systemic infection (e.g. urinary tract infection (UTI), active pneumonia) or evidence of any surgical site infection, fever $> 38.3^{\circ}\text{C}$, positive blood culture and/or a positive chest x-ray for acute infectious process
 6. Subject will require use of dural adhesive or sealant
 7. Subject is intended to undergo craniectomy wherein bone flap will not be returned
 8. Subject with suspected low success in wound healing due to past treatments (e.g. chemotherapy, radiation therapy, severe diabetes etc.) or other conditions (e.g. severe peripheral vascular disease, long standing steroids treatment)

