 9. Subject has been clinically diagnosed with malignancy (other than basal cell carcinoma or low-grade glioma), uncontrolled diabetes ($\text{A1C}>6.5\%$), sepsis, systemic collagen disease.
 10. Subject had chemotherapy and/or radiotherapy in the past 12 weeks before surgery or is planned to have chemotherapy or radiotherapy less than 12 weeks after surgery.
 11. Subject is an acute cranial trauma surgical case
 12. Subjects with a concurrent disease that would place the patient in excessive risk to the planned surgery
 13. Subject had a previous neurosurgery in the same

anatomical site

14. Subject with other undesirable symptoms defined by the principal investigator
15. Patient has clinically significant coagulopathy as determined by the surgeon
16. Subject is participating in another clinical trial using similar investigational devices/drugs

Visits and Procedures

Baseline: The baseline visit will include an assessment of subject qualifications for inclusion in the study according to the inclusion/exclusion criteria. Informed consent must be signed. Medical data will be taken including subject's medical complaints, medical history, neurological assessment, and medications use. Blood tests will include CBC and chemistry (according to site standards).

Randomization and Procedure: Vital signs (blood pressure, temperature, pulse rate), as well as height and weight will be measured prior procedure.

The subject will be randomized during the index procedure after the physician confirmation that the subject fulfills all inclusion criteria. If found eligible, subject will be enrolled and randomized to one of the 2 groups: experimental group (ArtiFascia device recipients) or control group (commercially available suturable dural substitutes recipients). In addition, recruitment of subjects planned to undergo surgery in posterior fossa area will be limited to 15% of the total study sample size to ensure comparability to common rates of this procedure reported in the literature.

Procedure will be performed under general anesthesia. ArtiFascia® or the control device will be implanted and sutured according to device IFU. Immediately post procedure essential data will be recorded including procedural details, surgeon's opinion on device ease of use and suture-ability, and other procedure related complications and medications prescribed.

Post operation the subject will stay at the hospital according

to site standards and physician discretion.

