STATISTICAL ANALYSIS PLAN (SAP)

Study No.: **CLN-01-1011 (NEOART)**

Study Title: **A Prospective, randomized, controlled multi-center study of ArtiFascia® Dural repair patch compared with commercially available dural substitutes.**

Device: **ArtiFascia®**

Intended Use: **ArtiFascia® is indicated as a dural substitute for the repair of dura matter.**

Date: **14AUG2022**

Version: **Version 2.0**

NCT: **04145544**

Sponsor: **Nurami Medical Ltd.
[name]**

Statistical Considerations

Randomization

Eligible Subject will be randomly allocated into one of the two treatment groups by Interactive Response Technology (IRT) in a 2:1 allocation ratio of ArtiFascia and control group respectively, using blocks stratified by study sites and surgery in posterior fossa area or not.

The primary endpoint will be absence of CSF fistula (drainage from wound or sinus) and pseudo-meningocele within 6 months post-operative evaluated by Magnetic Resonance Imaging evaluation and physical examination of the surgical site.

Sample Size Rationale

The sample size for this study is calculated assuming the following assumptions: power of 80%, 5% one-sided significance level, 2:1 allocation ratio of ArtiFascia and control groups respectively, the absence of CSF leak rate in both the ArtiFascia and control groups is 97%, non-inferiority margin of -10% and the Chi-square test statistics.

Assuming the above assumptions a sample size of 81 subjects will be required in total. Allowing for a potential 10% dropout, 90 subjects should be randomized (60 in the ArtiFascia® group and 30 in the control group).

Blinded Sample Size Reassessment

To examine whether the assumed absence of CSF leak rate of 97% in the sample size calculation, a non-comparative assessment of the pooled absence of CSF leak rate will be performed after 50% of the randomized subjects will complete the study.

In case that the pooled absence of CSF leak rate will be less than the assumed 97%, the sample size will be upsized accordingly.

Primary Efficacy Endpoint Analysis

The primary endpoint: CSF leakage absence at month 6 will be tested for non-inferiority of the CSF leakage absence rate in the ArtiFascia group, to that in the control group, using a non-inferiority margin of -10%.

The estimated rates of CSF leakage absence at month 6 for each treatment group and the difference between the treatment groups (ArtiFascia - Control) will be calculated.

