Exact one-sided 95% confidence interval will be calculated for the difference between the treatment groups in CSF leakage absence rates at month 6 using the Farrington-Manning method.

Non-inferiority will be concluded if the lower limit of the one-sided 95% exact confidence interval of the difference between the two study arms of CSF leakage absence rate at month 6 will be above the non-inferiority margin of -10%.

Secondary Efficacy Endpoints

The following secondary efficacy endpoints will be compared between the study treatment groups using Fisher exact test (for endpoints with more than 2 categories, collapsing of categories with low frequency will be considered):

1. Wound healing assessment (Clean and/or fully healed vs. Infected),) which will be considered as key secondary efficacy end point
2. Device Handling Characteristics (Ease of Use, Strength, Suturability, Seal Quality)
3. Magnetic Resonance Imaging at the 6-month follow-up, to determine the presence or absence of the following measures:
 - Adhesion formation
 - New tissue formation
 - Brain edema adjacent to device implant site

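### Device handling is tested with a pooled Fisher test although randomisation is stratified by site; if ratings differ between sites, the test stays valid but loses power

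*SAP*

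**What the plan says.** - **Design.** SAP, Randomization: allocation is 2:1, "using blocks stratified by study sites and surgery in posterior fossa area or not". Block size is not given.
- **Sites.** Protocol synopsis, Investigational sites: "Up to 10 centers in Europe and Israel are planned to participate in this study".
- **Raters.** Protocol synopsis, Randomization and Procedure: the data recorded straight after surgery include the "surgeon's opinion on device ease of use and suture-ability". That names two of the four handling items. Neither document says who rates strength or seal quality.
- **Analysis.** SAP, Secondary Efficacy Endpoints: the listed endpoints, with handling as item 2, "will be compared between the study treatment groups using Fisher exact test". For endpoints with more than two categories, "collapsing of categories with low frequency will be considered". No stratified test or site term is named. The rating scale and the sidedness of the test are not stated.
- **Standing of the endpoint.** Wound healing is the key secondary endpoint. Handling has no stated power and no success rule.

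**The concern.** A handling score is a personal judgement. A lenient surgeon tends to score both devices high and a strict one to score both low. Blocking within site means that each site should use both devices in roughly 2:1 proportion, so site leniency largely cancels from the difference between arms. The pooled Fisher test does not use this. It judges the difference against total variation, including the between-site part that the design has already balanced out.

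The real type I error then falls below the nominal level and power falls with it. What is at stake is a real handling difference, in either direction, that could be missed. A non-significant result on a disadvantage could also be read as reassurance.

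**Working it through.** **1. The plan's own figure.** The only sample size stated is for the primary endpoint ("power of 80%, 5% one-sided significance level, 2:1 allocation ratio of ArtiFascia and control groups respectively", 97% in both arms, margin 10 points). Control n = (1.645 + 0.842)² × 0.97 × 0.03 × (1 + 1/2) / 0.10² = 6.18 × 0.04365 / 0.01 ≈ 27. The test arm has 54, so the total is 81, and 81/0.9 = 90. The figure reproduces, but it says nothing about handling.

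**2. Mechanism.** Let ratings have within-site SD 1 and between-site SD s. With arms balanced within site, the true variance of the arm difference is about 1/(1 + s²) of what a pooled test assumes.
- s = 0.5: intraclass correlation 0.25/1.25 = 20%. The critical value 1.96 acts like 1.96/√0.80 = 2.19, a two-sided level of about 2.8%.
- s = 0.8: intraclass correlation 0.64/1.64 = 39%. It acts like 1.96/√0.61 = 2.51, about 1.2%.

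This is a rough guide for a continuous score. Categorising the rating dilutes the effect.

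**3. Simulated power.** Assumptions, because the documents give no values: 10 sites of 9 subjects at 6:3, device effect 0.6 SD on a latent unit-SD scale, two-sided 5%. Where two figures are shown they come from separately coded runs, with 2,500 or 3,000 trials per setting where the count is known. At 3,000 trials the Monte Carlo standard error is about √(0.4 × 0.6/3000) = 0.9 points.

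| Site SD | Binary: Fisher | Binary: exact, site-stratified | Binary: asymptotic CMH | Ordered: Wilcoxon | Ordered: van Elteren |
|---|---|---|---|---|---|
| 0 | 55% | 54% | 57% | 70% | 68% |
| 0.5 | 45%, 46% | 48%, 50% | 54% (first run) | 61%, 60% | 66%, 65% |
| 0.8 | 35%, 37% | 43%, 45% | 48%, 50% | 51%, 51% | 67%, 66% |

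Fisher against the exact stratified test isolates site for a binary rating: 3 to 4 points at SD 0.5 and 8 at SD 0.8. Wilcoxon against van Elteren isolates it for an ordered rating: about 5 and 15 points. From the exact stratified test to asymptotic CMH there are a further 5 points at SD 0.8 (48 − 43; 50 − 45). These come from the discreteness of exact tests and not from site.

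With about 90% of control ratings favourable, Fisher has 16% and the exact stratified test 17% at SD 0.8; at SD 0.5 both have 21%.

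**4. Type I error.** At site SD 0.8 and no device effect, Fisher rejects in 1.8% to 2.2% of trials and asymptotic CMH in 4.8% to 4.9%. The unstratified Wilcoxon test, which does not share Fisher's discreteness, rejects in 1.9% to 2.1% and van Elteren in 4.9% to 5.2%.

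**5. A second model.** Binary ratings had a site effect on the logit scale, 5 or 10 sites of equal or unequal size, 50% to 90% favourable in controls, and log odds ratio 1.4. The power change from Fisher to exact stratified CMH was:

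| Logit site SD | 0 | 0.5 | 1 | 1.5 | 2 |
|---|---|---|---|---|---|
| Change, points | −3 to 0 | −3 to +1 | 0 to +4 | +2 to +10 | +5 to +15 |

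A logistic residual has SD π/√3 = 1.81, so latent SDs of 0.5 and 0.8 correspond to logit SDs of about 0.9 and 1.5. The two models agree. Fisher's type I error never exceeded 4.8% and fell to 1.2% to 1.9% at logit SD 2.

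**The case against.** The strongest reply is that this is a preference about efficiency and not an error.

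- **The driving quantity is assumed.** The documents give no between-site variation, scale, site sizes or number of surgeons. A site SD of 0.8 implies an intraclass correlation of 39%, which is large. At small site effects the gain is negligible. This stands, and it makes the size of the point conditional.
- **Fisher against asymptotic CMH exaggerates.** A reader might credit the whole gap of about 13 points at SD 0.8 (48 − 35) to ignoring site. Only about 8 of these belong to site.
- **Only two items are documented as surgeon opinion.** Treating strength and seal quality the same way is an assumption.
- **A conservative test is not a wrong one.** A reader might infer that the p-values are invalid or that false positives rise. The documents do not support that, and the simulations show the reverse.
- **Little hangs on handling.** It has no power target and no success rule.

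These limits reduce the weight of the point but do not remove it. The trial already randomises by site, so analysing by site needs no new data. The possible loss is small beside the possible gain.

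**Conclusion.** The point holds as a conditional loss of efficiency. The pooled Fisher test is valid but conservative if ratings differ between sites, and the possible gain from stratifying ranges from none to about 8 points for a binary rating and about 15 for an ordered one over the site SDs of 0 to 0.8 examined. The logit model reaches 15 points for a binary rating only at its largest site effect.

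This rests on the assumed site sizes, device effect and between-site SD, on a two-sided 5% test, and on the surgeon rating all four items. It also treats rater differences as site differences. If several surgeons operate at one site, stratifying by site removes only part of the rater variation.

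A reader might go further and conclude that real handling differences will be missed. The documents do not support that without a figure for between-site variation. The sample size and the primary non-inferiority conclusion are unaffected.

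**What to change.** In SAP, Secondary Efficacy Endpoints, for the handling items only:

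1. Replace the pooled Fisher test with a site-stratified test, with exact or within-site permutation p-values. Use CMH if the rating is binary or unordered, and van Elteren or CMH row-mean-score if it is ordered. State the scale, the sidedness and the alpha.
2. Stratify by site only. Posterior fossa cases are "limited to 15% of the total study sample size", so at most 13 of 90 (0.15 × 90 = 13.5). Over 10 sites that is about one per site, too sparse to cross with site.
3. Pre-specify a rule for pooling very small sites.
4. Report the site-stratified difference with its confidence interval.
5. State who rates strength and seal quality.

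The cost is SAP wording and a few lines of code. Sites that used only one device contribute nothing unless pooled. If raters do not differ, about 1 to 2 points of power are lost, and up to about 3 in some of the logit settings.

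### Device handling ratings are almost certainly ordered, yet the SAP tests them with Fisher's exact test and leaves category merging open; a rank-sum test on the full grades would serve better

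*SAP*

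**What the plan says.** Under Secondary Efficacy Endpoints, the SAP says that the listed endpoints "will be compared between the study treatment groups using Fisher exact test", with the proviso that "for endpoints with more than 2 categories, collapsing of categories with low frequency will be considered". It gives no frequency threshold, no restriction to neighbouring grades, no timing, and no statement on whether pooled counts or counts by arm guide the merging.

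Three groups of endpoints follow:

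- Item 1 is written with two outcomes, "Wound healing assessment (Clean and/or fully healed vs. Infected", and is the one "which will be considered as key secondary efficacy end point".
- Item 2 is "Device Handling Characteristics (Ease of Use, Strength, Suturability, Seal Quality", with no response levels.
- Item 3 uses MRI "to determine the presence or absence of the following measures", so each measure has two levels.

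The protocol synopsis (Visits and Procedures, Randomization and Procedure) says that "surgeon's opinion on device ease of use and suture-ability" is recorded immediately after the operation. It gives no scale either.

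**The concern.** Items 1 and 3 are analysed as two categories, so the clause on more than two categories has only the handling items left to govern. Such ratings would normally be graded. On a table with several columns, Fisher's exact test treats the grades as interchangeable labels, and two things follow. A small p-value may reflect a difference in spread with no difference in level. A consistent shift towards better ratings is harder to detect than it need be.

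The merging clause adds a second, smaller problem. Which grades are joined can change the p-value, and the SAP leaves that choice open until the data are seen. At stake is how the handling results can be read. The trial's main conclusion is not at stake.

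**Working it through.** **The plan's own figure.** The only calculated number in the documents is the primary sample size. Inputs from the SAP's Sample Size Rationale: "power of 80%, 5% one-sided significance level, 2:1 allocation ratio of ArtiFascia and control groups respectively", 97% in both arms, margin 10 points.

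Control n = (1.645 + 0.842)² × 0.97 × 0.03 × (1 + 1/2) / 0.10² = 26.99, so 27. ArtiFascia n = 54, total 81, and 81/0.9 = 90. This reproduces the plan. No calculation is given for handling. Because handling is rated at surgery, the checks below use all 60 and 30 patients.

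**Assumptions not in the documents:** three to five ordered grades, the control distributions shown, a proportional-odds shift in favour of ArtiFascia, and two-sided 5% tests.

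**Step 1: what ignoring order does.** Two illustrative tables, worst to best grade:

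| ArtiFascia (60) | Control (30) | Fisher p, all grades | Exact rank-sum p |
|---|---|---|---|
| 15/15/15/15 | 2/13/13/2 | 0.008 | 1.0 |
| 3/9/18/30 | 3/7/12/8 | 0.16 | 0.038 |

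There are 60 × 30 = 1,800 patient pairs. The probability that ArtiFascia is rated higher counts ties as half.

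- First table: ArtiFascia is higher in 15×2 + 15×15 + 15×28 = 675 pairs and tied in 15×30 = 450. The probability is (675 + 225)/1,800 = 0.50. Neither device is rated higher, yet Fisher's test is significant.
- Second table: ArtiFascia is higher in 9×3 + 18×10 + 30×22 = 867 pairs and tied in 9 + 63 + 216 + 240 = 528. The probability is (867 + 264)/1,800 = 0.63. ArtiFascia is rated higher, and Fisher's test misses it.

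**Step 2: power at odds ratio 2.5** (1,000 to 5,000 simulated trials per row):

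| Assumed control distribution, % | Fisher, all grades | Rank-sum | Gain, points |
|---|---|---|---|
| 5/10/25/35/25 | 46% | 60% | 14 |
| 5/10/20/35/30 | 48% | 61% | 13 |
| 10/20/40/30 | 47% | 60% | 13 |
| 5/15/40/40 | 46% | 56% | 10 |
| 2/3/15/80 | 31% | 33% | 2 |
| 5/15/80 | 28% | 29% | 1 |
| 3/12/85 | 24% | 25% | 1 |

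At odds ratio 3.5, on the second to fourth scales, Fisher has 74-75% power and the rank-sum test 82-85%. With no difference on those same scales, false positives are 4.4-5.0% for Fisher and 4.7-5.6% for rank-sum, both compatible with 5% given simulation error. The gain is largest when ratings spread over four or five grades. It nearly vanishes when most sit in the top grade, where differences of 1-2 points are within simulation error.

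**Step 3: merging** (the same three scales).

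- Merging neighbouring grades whose pooled count is below 9 (10% of 90) leaves false positives at 4.8-5.0%. Fisher's test conditions on the pooled totals, so a rule based only on those totals does not disturb it.
- Taking the smallest p-value over all two-level cuts and the full table, with results by arm in view, gives 10.2%, 11.3% and 11.8% per item.
- The choice of cut matters even without a search. At odds ratio 2.5, a single fixed two-level cut has power from 8% to 49%. In the second table of Step 1 the three cuts give p = 0.40, 0.20 and 0.043.

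**The case against.** The strongest reply is that the premise is inferred. The documents give no levels for the handling items and never call them ordered, and the form that defines them is not among the documents. The collapsing clause is generic, and wound healing may itself have been recorded on more than two levels before being written as two. This stands as a limit: the point is conditional on an ordered scale, and if the items are yes/no nothing is gained. But the clause anticipates some endpoint with more than two categories, and handling is the only listed one not already analysed as two.

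It is also fair that Fisher's test is valid, that the size of the power loss depends on an unseen scale, and that proportional odds is the setting that suits a rank test.

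Three stronger readings are tempting, and the documents do not support them:

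- **That the data will choose a responder cut.** No responder analysis or good/poor boundary is planned, merging a sparse grade need not leave two levels, and the stated trigger is low frequency, not the result by arm. The 10-12% figure describes a practice that the SAP does not exclude, not one that it plans.
- **That the comparison has no direction.** The p-value from an unordered table with several grades has none, but the distributions by arm would show it, and a collapsed two-by-two table has one.
- **That a claim of comparable handling fails because Fisher's test is used.** A non-significant rank-sum test would not show comparability either. Nor does changing the test deal with the surgeon's knowledge of which device was implanted.

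**Conclusion.** The concern holds as a conditional point of efficiency and interpretation. If the handling items have more than two ordered grades, as is almost certain where the collapsing clause applies, the planned test discards the order. The cost with 60 and 30 patients is about 0 to 14 points of power under the assumed scales, plus the possibility of a significant result that reflects spread alone. False positives stay near 5% if any merging rests on pooled counts. They reach about 10-12% per item only if the cut is selected with results by arm visible.

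These sizes rest on assumed scales, distributions and proportional odds. Handling is not the key secondary endpoint and has no power target in the SAP. The primary non-inferiority conclusion and the 81/90 sample size are unaffected. The change is worth making because it costs little.

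**What to change.** In the SAP, under Secondary Efficacy Endpoints:

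1. State the response scale of each handling item and the order of its grades.
2. For items with more than two ordered grades, replace Fisher with collapsing by an exact Wilcoxon rank-sum test on the uncollapsed grades. It copes with sparse grades, so the merging clause is no longer needed for these items.
3. Report the full distribution by arm and the probability that an ArtiFascia rating exceeds a control rating (ties counted as half), with its 95% CI.
4. If a two-level summary is wanted, name the favourable grades before unblinding.
5. Keep Fisher's exact test for the two-category endpoints.

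The cost is a few sentences, with no new data or patients. The one statistical downside is that the rank test has less power against a difference in spread that does not shift the level; the tabulated distributions would still show such a difference.
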